2. TRIAL OBJECTIVES AND ENDPOINTS

2.1 MAIN OBJECTIVES, PRIMARY AND SECONDARY ENDPOINTS

2.1.1 Main objectives

The main objective of this trial is to investigate the effect of multiple oral dosing of 10 mg BI 1467335 over 28 days and multiple oral dosing of 3 mg BI 1467335 over 42 days on MAO-B occupancy in the brain compared to baseline using [¹¹C]-L-deprenyl-D2 PET tracer in healthy male subjects.

2.1.2 Primary endpoint

The following primary endpoint will be determined:

- % reduction in MAO-B availability upon treatment with BI 1467335 on the last treatment day (Day 28 for the 10 mg dose group and Day 42 for the 3 mg dose group) compared to baseline.

2.1.3 Secondary endpoints

The following secondary endpoints will be determined:

- % reduction in MAO-B availability upon treatment with 10 mg BI 1467335 on Day 14 compared to baseline.
- % reduction in MAO-B availability upon treatment with 3 mg BI 1467335 on Day 28 compared to baseline.
- MAO-B inhibition in platelet rich plasma at Day 14 (10 mg dose group only), Day 28, and Day 42 (3 mg dose group only) compared to baseline.
- $C_{max,N}$ (maximum measured concentration of the analyte) and $AUC_{0-24,N}$ (area under the concentration-time curve of the analyte over the time interval from 0 to 24 h) on Day 14 (10 mg dose group only), Day 28 and Day 42 (3 mg dose group only).

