		649:30	10:30			x	x	x			
		651:00	12:00			x					
		652:00	13:00	Lunch, 240 mL water intake ³		x					
		655:00	16:00	Snack ³		x					
		657:00	18:00	Dinner ³					x	x	
	29	672:00	09:00	Discharge from trial site and confirmation of fitness ¹²	x				x	x	
3	33-36			End of trial (EoTrial) examination ^{6, 7}	x				x	x	x

1. Subject must be informed and written informed consent obtained prior to starting any screening procedures. Screening procedures include physical examination, check of vital signs, ECG, safety laboratory (including drug, alcohol, nicotine and virus screening), demographics (including determination of body height and weight, BMI, smoking status and alcohol history), relevant medical history, concomitant therapy and review of inclusion/exclusion criteria. In case subject is considered eligible for study participation, an MRI will be conducted as part of the screening procedures.
2. The time is approximate; the procedure is to be performed and completed within a time window of 3 h prior to drug administration. After start of treatment on Day 1, further predose PK blood sampling should be performed within 30 minutes before next scheduled dosing.
3. If several actions are indicated at the same time point, the intake of meals will be the last action.
4. Subjects are to be fasted for at least 10 h before sample is taken.
5. Only urine drug, alcohol screening and assessment of urine cotinine to confirm no smoking will be done at this time point.
6. End-of-trial (EoTrial) examination to be performed on Day 33-36, EoTrial examination includes physical examination, vital signs, ECG, safety laboratory, recording of AEs and concomitant therapies.
7. For definition of the individual subject's end of trial see [Section 6.2.3](#).
8. Dynamic PET scan will be acquired from 0 to 90 minutes after injection of the PET ligand [¹¹C]-L-deprenyl-D2. In parallel arterial blood samples will be collected continuously for 15 min using an automated blood sampling system at a speed of 5 mL/min. In addition, arterial blood will be drawn manually at several time points during the PET scan
9. Subjects will be hospitalized from admission on Day -1 up to Day 29.
10. AEs and concomitant therapies will be recorded throughout the trial, but will be specifically asked for at the times indicated in the [Flow Chart](#) above.
11. On trial days 14 and 28, subjects will be allowed a light breakfast after safety assessments have been completed.

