7.3 PLANNED ANALYSES

Analysis sets

Statistical analyses will be based on the following analysis sets:

- Treated set (TS): The treated set includes all subjects who were randomized and treated with at least one dose of study drug. The treated set will be used for safety analyses.
- Pharmacokinetic parameter analysis set (PKS): This set includes all subjects in the treated set (TS) who provide at least one PK endpoint and was not excluded due to a protocol deviation relevant to the evaluation of PK or due to PK non-evaluability (as specified in the following subsection ‘Pharmacokinetics’). Thus, a subject will be included in the PKS, even if he/she contributes only one PK parameter value to the statistical assessment. Analyses of PK parameters will be based on the PKS.
- PET set (PETS): This set includes all subjects in the treated set (TS) who provide at least one PET scan at baseline and one on-treatment.

Adherence to the protocol will be assessed by the trial team. Important protocol deviations (iPD) categories will be suggested in the integrated risk management plan (IQRMP), iPDs will be identified no later than in the Report Planning Meeting, and the iPD categories will be updated as needed.

Pharmacokinetics

The pharmacokinetic parameters listed in [Section 2.1](#) and [2.2](#) for BI 1467335, will be calculated according to the relevant SOP of the Sponsor [[001-MCS-36-472](#)].

Plasma concentration data and parameters of a subject will be included in the statistical pharmacokinetic (PK) analyses if they are not flagged for exclusion due to a protocol deviation relevant to the evaluation of PK (to be decided no later than in the Report Planning Meeting) or due to PK non-evaluability (as revealed during data analysis, based on the criteria specified below). Exclusion of a subject's data will be documented in the CTR.

Relevant protocol deviations may be

- Incorrect trial medication taken, i.e. the subject received at least one dose of trial medication the subject was not assigned to
- Incorrect dose of trial medication taken
- Use of restricted medications

Plasma concentrations and/or parameters of a subject will be considered as non-evaluable, if for example

- The subject experienced emesis that occurred at or before two times median t_{max} of the respective treatment (median t_{max} is to be determined excluding the subjects experiencing emesis),
- Missing samples/concentration data at important phases of PK disposition curve

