7.3.2 Secondary endpoint analyses

Secondary endpoints:

- % reduction in MAO-B availability upon treatment with 10 mg BI 1467335 on Day 14 compared to baseline.
- % reduction in MAO-B availability upon treatment with 3 mg BI 1467335 on Day 28 compared to baseline.
- MAO-B inhibition in platelet rich plasma at Day 14 (10 mg dose group only), Day 28 and Day 42 (3 mg dose group only) compared to baseline.

Will be analysed similarly to the primary endpoints described in [Section 7.3.1](#) above.

The secondary endpoints C_{\max} and AUC_{0-24} of BI 1467335 will be only evaluated descriptively. The following descriptive statistics will be calculated: N, arithmetic mean, standard deviation, minimum, median, maximum, arithmetic coefficient of variation, geometric mean, and geometric coefficient of variation. The data format for descriptive statistics of concentrations will be identical with the data format of the respective concentrations. The descriptive statistics of PK parameters will be calculated using the individual values with the number of decimal places as provided by the evaluation program. Then the individual values as well as the descriptive statistics will be reported with 3 significant digits in the clinical trial report.

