7.5.2 Pharmacokinetics

Handling of missing PK data will be performed according to the relevant Corporate Procedure [[001-MCS-36-472](#)].

PK parameters that cannot be reasonably calculated based on the available drug concentration-time data will not be imputed.

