## **6.6 HANDLING OF MISSING DATA AND OUTLIERS**

Data of screened subjects who were withdrawn from the trial prior to first administration of investigational study drug will not be reported in the CTR.

Data of subjects who drop out or withdraw from the trial will be reported in the CTR as far as their data are available. All withdrawals will be documented and the reason for withdrawal reported in the CTR.

**CTP Section 7.5.1:** *It is not planned to impute missing values for safety parameters.*  
One exception where imputation might be necessary for safety evaluation are AE dates.  
Missing or incomplete AE dates are imputed according to BI standards.

**CTP Section 7.5.2:** *PK parameters that cannot be reasonably calculated based on the available drug concentration-time data will not be imputed.*  
Missing data and outliers of PK data are handled according to BI standards ([4](#)).

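### The 10 mg Flow Chart marks no PK sample later than 7 h after the Day 28 dose, although AUC0-24 on Day 28 is a secondary endpoint for that group

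*Protocol*

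**What the plan says.** **Endpoint.** Protocol 2.1.3, repeated in SAP 5.2.2, lists AUC0-24,N, the "area under the concentration-time curve of the analyte over the time interval from 0 to 24 h". It is required on Day 14 for 10 mg only, on Day 42 for 3 mg only, and on Day 28 without restriction. Protocol 7.3.2 says that Cmax and AUC0-24 "will be only evaluated descriptively".

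**Schedule.** Protocol 5.3.1 takes the PK sampling times from the Flow Chart. In the 10 mg chart, Day 28 PK marks run from predose (648:00) to 655:00. The 657:00 row has ECG and vital-sign marks only. The next row is Day 29, 672:00, labelled "Discharge from trial site and confirmation of fitness". It has safety laboratory, ECG and vital-sign marks and an empty PK cell. Footnote 2 adds: "After start of treatment on Day 1, further predose PK blood sampling should be performed within 30 minutes before next scheduled dosing". Footnote 9 says: "Subjects will be hospitalized from admission on Day -1 up to Day 29".

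**Handling.** Protocol 7.3 calculates PK parameters under a sponsor SOP and gives as an example of non-evaluability: "Missing samples/concentration data at important phases of PK disposition curve". Protocol 7.5.2 refers missing PK data to the same procedure and adds that "PK parameters that cannot be reasonably calculated based on the available drug concentration-time data will not be imputed". SAP 6.6 says: "Missing data and outliers of PK data are handled according to BI standards". SAP 3 specifies noncompartmental analysis and states no rule for a profile that stops before 24 h.

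**The concern.** An area over 24 h cannot be observed from samples that stop at 7 h. The remainder has to be extrapolated, or closed with the Day 28 predose value standing in for the 24 h concentration, or the parameter has to be left out. Each choice gives a different number or none. Read literally, the non-evaluability example and the no-imputation rule could leave the 10 mg Day 28 value unreported for all five subjects.

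The stop at 7 h looks more like an omission than a design choice. The same group's Day 14 profile goes to 24 h, and even the 3 mg profile on its last dosing day keeps an 11 h mark.

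At stake is how the two 10 mg AUC0-24 values can be read. Protocol 3.2 uses the intermediate PET day to see whether inhibition holds as systemic exposure rises. Day 14 and Day 28 AUC0-24 describe that rise in exposure, and they would be tabulated for the same five men on different bases.

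**Working it through.** **1. Time after dose of each marked PK sample** (Flow Chart clock minus dose clock)

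| Profile | Dose at | PK marks | Last mark | Unsampled part of 24 h |
|---|---|---|---|---|
| 10 mg Day 14 | 312:00 | 10 | 336:00 = 24 h | 0 h |
| 10 mg Day 28 | 648:00 | 8 | 655:00 = 7 h | 24 − 7 = 17 h (17/24 = 71%) |
| 3 mg Day 28 | 648:00 | 10 | 672:00 = 24 h | 0 h |
| 3 mg Day 42 | 984:00 | 9 | 995:00 = 11 h | 24 − 11 = 13 h (13/24 = 54%) |

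Protocol 6.1 allows ±2 h on PET days. A 7 h sample taken at 9 h still leaves 15/24 = 62.5% unsampled. The 3 mg Day 42 row is less informative, because its 1008:00 line (24 h after the dose) is merged with the Day 47-50 visit in the text.

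**2. Can footnote 2 supply the 24 h sample?** It times a predose sample against the next dose. Dosing in the 10 mg group ends on Day 28, so the footnote creates no Day 29 sample. It does not forbid one either.

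**3. Scale, under assumptions.** The drug-profile section as available gives no half-life, so there is no figure in the plan to reproduce. Assume a one-compartment oral profile at steady state with τ = 24 h:

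C(t) ∝ ka/(ka − k) × [e^(−kt)/(1 − e^(−kτ)) − e^(−ka·t)/(1 − e^(−ka·τ))]

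Half-lives are 1, 2, 3, 4, 6, 8, 12, 16 and 24 h, and absorption half-lives 0.15, 0.3 and 0.6 h, which gives 27 profiles. Share of AUC0-24 after 7 h: 0.009 to 0.650.

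Next, close the Day 28 profile with predose as C24 and divide by the AUC from the Day 14 schedule, with the same true exposure on both days:

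- Linear-up/log-down: 1.000 throughout.
- Linear: 1.007 to 1.180. By half-life: 1 h, 1.037-1.074; 2 h, 1.138-1.180; 3 h, 1.145-1.170; 4 h, 1.121-1.136; 6 h, 1.077-1.083; 12 h, 1.026-1.027; 24 h, 1.007.

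**4. Hand check of the tail.** Take a half-life of 3 h, so k = 0.2310, and set C7 = 1. Then C11 = 2^(−4/3) = 0.397 and C24 = 2^(−17/3) = 0.0197.

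- Log rule, 7 to 24 h in one step: (1 − 0.0197)/0.2310 = 4.24. With the 11 h point: (1 − 0.397)/0.2310 + (0.397 − 0.0197)/0.2310 = 2.61 + 1.63 = 4.24. The 11 h sample changes nothing.
- Linear rule, one step: 17 × (1 + 0.0197)/2 = 8.67. With the 11 h point: 4 × (1 + 0.397)/2 + 13 × (0.397 + 0.0197)/2 = 2.79 + 2.71 = 5.50. The one-step tail is 3.17 units larger.

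**5. If steady state is not quite reached.** Suppose predose is 10% below the true C24 (assumed). The log-down ratio to the Day 14 basis is then 0.969 to 1.000.

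**The case against.** The strongest reply is that the evidence is a damaged chart. In the 10 mg chart the Day 14 rows are shifted, the labels for Days 16-22 are missing, and in the 3 mg chart the discharge row is fused with the end-of-trial visit. A 659:00 row could have been lost in the same way. That stands for the 11 h sample. It is weaker for the 24 h sample, because the 672:00 row survives with its other marks in place.

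Second, the amendment log in Protocol 11.1 records that a discrepancy in the planned 10 mg PK time points was corrected for this version. So the schedule was looked at. The entry does not say which time points changed, so it does not settle the matter.

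Third, a reader might infer that the plan has no way of handling the gap. The documents do not support that. Protocol 7.3 and 7.5.2 and SAP 6.6 refer PK calculation and missing data to sponsor procedures, which may contain a rule. What can be said is that the available text states none, and that the visible provisions address missing data and parameters that cannot be calculated. They do not address a schedule that plans no sample.

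Fourth, the sizes come from assumed profiles, and the most favourable rule shows no difference. That is fair, so the 18% is no estimate of bias in this trial.

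**Conclusion.** The endpoint and the 10 mg schedule do not match in the text as it stands: AUC0-24 is required on Day 28, and 17 of the 24 h have no marked sample. The finding is conditional on the source chart, firmly for the 11 h mark and less so for the 24 h mark.

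The size cannot be fixed from the documents. With predose as C24 and one-compartment decline, the Day 28 basis equals the Day 14 basis under log-down and exceeds it by 0.7% to 18% under linear. That equality rests on single-exponential decline and on steady state. Protocol 3.2 claims steady state, but it also describes exposure that increases over time.

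The consequence is minor: one descriptive secondary endpoint in five subjects. A reader might infer that the Day 14 to Day 28 exposure comparison, or the PET result, is compromised. Neither follows. No test of Day 14 against Day 28 AUC is planned, and Protocol 7.3.1 relates occupancy to the concentration at scan time. The PET primary endpoint, the concentration-occupancy model and the decision on the 3 mg group do not use AUC0-24. Cmax is affected only if the peak falls after 7 h.

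**What to change.** 1. Check the 10 mg Day 28-29 rows in the source Flow Chart, and the 3 mg Day 42-43 rows at the same time. If the 11 h and 24 h marks are there, the point closes. Cost: minimal.
2. If the 10 mg marks are absent and sampling is not finished, add PK samples at 659:00 and 672:00 to match that group's Day 14 schedule. Define the second as 24 h after the Day 28 dose, because footnote 2 refers to a following dose that does not exist here. Cost: 2 × 5 = 10 samples of about 3 mL, 30 mL in total. The subjects are still in-house, and a safety laboratory assessment is already due at 672:00. Which sample matters more depends on the interpolation rule in the sponsor procedure, so both are proposed.
3. If sampling is complete, name in the SAP the procedure clause or rule used for 7-24 h, including the interpolation method and any steady-state assumption. Label the 10 mg Day 28 AUC0-24 as resting on a different basis from Day 14. Cost: a few sentences.

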3. DESCRIPTION OF DESIGN AND TRIAL POPULATION

3.1 OVERALL TRIAL DESIGN AND PLAN

The study will be performed as a non-randomised, open-label, parallel-group, multiple dose trial in healthy male subjects in order to investigate the effect of multiple oral doses of 10 mg BI 1467335 administered once daily over 28 days and of 3 mg BI 1467335 administered once daily over 42 days on MAO-B activity in the brain. The MAO-B activity will be assessed by means of a dynamic PET scan using [¹¹C]-L-deprenyl-D2 PET as tracer. PET scans will be conducted predose and on Day 28 for both dose groups. An additional PET scan will be conducted on Day 14 in the 10 mg dose group and on Day 42 in the 3 mg dose group. On these days, subjects will be injected with the radiotracer and subsequently undergo dynamic PET scans. In addition to PET scan, MAO-B activity will be also measured in platelet rich plasma.

For the 10 mg dose group, subjects will be hospitalised from Day -1 to Day 29.

For the 3 mg dose group, subject will be hospitalised from Day -1 to Day 43. The subjects will be allowed to leave the clinical unit in the afternoon on Day 7 and Day 14.

The 10 mg dose group will be investigated first. In case no MAO-B inhibition is seen in this dose group, the 3 mg dose group will not be further investigated.

The oral treatments will consist of either two 5 mg or three 1 mg film-coated tablets (dose strength based on free base) for subjects dosed with 10 mg and 3 mg BI 1467335, respectively. The treatments will be administered once daily for 28 days for the 10 mg dose groups and once daily for 42 days for the 3 mg dose groups. The subjects willing to participate can choose convenient visit dates on a first-come, first-served basis: as soon as 5 subjects have been allocated to 1 of the 2 dose groups, the following subjects will be allocated to the other dose group. For details, refer to [Section 4.1](#).

An overview of all relevant trial activities is provided in the [Flow Chart](#). For visit schedule and details of trial procedures at selected visits, refer to [Sections 6.1](#) and [6.2](#), respectively.

3.2 DISCUSSION OF TRIAL DESIGN, INCLUDING THE CHOICE OF CONTROL GROUP

The doses selected for this study, 10 mg BI 1467335 q.d. (2 film-coated tablets of 5 mg dose strength) and 3 mg BI 1467335 q.d. (3 film-coated tablets of 1 mg dose strength), have been used in healthy volunteers and shown to be well tolerated. The predose measurement will be used as a baseline, so no placebo dose is required in this study.

The planned dosing duration of 28 days for the 10 mg dose group and 42 days for the 3 mg dose group is long enough to reliably achieve steady-state drug exposures and to exclude any transient effects.

Due to the time dependent non-linear kinetics of BI 1467335, systemic exposures on Day 28 and Day 42 cannot be predicted from Day 1 kinetics (IB [[c04751792](#)]). Therefore the MAO-B inhibition in the brain will be determined on Day 28 and Day 42 after start of treatment

Proprietary confidential information © 2019 Boehringer Ingelheim International GmbH or one or more of its affiliated companies

with 10 mg and 3 mg BI 1467335, respectively, and compared to the individual baseline value to investigate the maximum inhibition. The *in vitro* data suggested an irreversible inhibition, which could potentially accumulate over time following multiple dosing and with the increase in exposure observed over time which characterizes BI 1467335 kinetics. The investigation on Day 14 for the 10 mg dose group and on Day 28 for the 3 mg dose group will evaluate whether the MAO-B inhibition reaches its maximum over the treatment duration and is maintained regardless of the increase in BI 1467335 systemic exposure. The 10 mg dose group will be investigated first. In the event no MAO-B inhibition is seen following the administration of 10 mg BI 1467335 daily over 28 days, the study will be considered as complete and no further investigation with a lower dose (3 mg) will be conducted.

[¹¹C]-L-deprenyl-D2 is a PET radioligand used for measurement of the MAO-B activity in the brain. This radioligand has been used for several PET studies to evaluate MAO-B inhibition in the brain in healthy subjects and is unlikely to exhibit any detectable isotope effects (see [Section 1.4](#)).

Because of the exposure with radioligands the study will only include male subjects.

The open-label treatment is not expected to bias results, since the study endpoints are derived from medical procedures and laboratory assessments with an unlikely relevant impact by subjective factors.

3.3 SELECTION OF TRIAL POPULATION

It is planned that 10 healthy male subjects (5 in each dose group) will enter the study. They will be recruited from the volunteers' pool of the trial site.

The current trial is designed to investigate the effect of multiple oral dosing of 10 mg BI 1467335 over 28 days and 3 mg BI 1467335 over 42 days on MAO-B inhibition in the brain. Healthy male subjects are an ideal population for the objectives of this trial, since they provide relatively stable physiological, biochemical and hormonal conditions, i.e. the absence of disease-related variations and relevant concomitant medications.

A log of all subjects enrolled into the trial (i.e. who have signed informed consent) will be maintained in the ISF irrespective of whether they have been treated with investigational drug or not.

3.3.1 Main diagnosis for trial entry

The study will be performed in healthy subjects.

3.3.2 Inclusion criteria

Subjects will only be included in the trial if they meet the following criteria:

Proprietary confidential information © 2019 Boehringer Ingelheim International GmbH or one or more of its affiliated companies

1. Healthy male subjects according to the assessment of the investigator, as based on a complete medical history including a physical examination, vital signs (BP, PR), 12-lead ECG, and clinical laboratory tests
2. Age of 21 to 55 years (inclusive)
3. BMI of 18.5 to 29.9 kg/m² (inclusive)
4. Signed and dated written informed consent prior to admission to the study, in accordance with GCP and local legislation
5. Non-smoker with no history of smoking
6. Subjects who are sexually active must use, with their partner, highly effective contraception from the time of administration of trial medication until 4 months after administration of trial medication. Adequate methods are:
 - Condoms *plus* use of hormonal contraception by the female partner that started at least 2 months prior to administration of trial medication (e.g., implants, injectables, combined oral or vaginal contraceptives, intrauterine device) *or*
 - Condoms plus surgical sterilization (vasectomy at least 1 year prior to enrolment) *or*
 - Condoms plus surgically sterilised partner (including hysterectomy) *or*
 - Condoms plus intrauterine device *or*
 - Condoms plus partner of non-childbearing potential (including homosexual men)

Subjects are required to use condoms to prevent unintended exposure of the partner to the study drug via seminal fluid.

Alternatively, true abstinence is acceptable when it is in line with the subject's preferred and usual lifestyle. If a subject is usually not sexually active but becomes active, with their partner, they must comply with the contraceptive requirements detailed above.

